#### 10.1.7. Data Quality Assurance

Participant data will be collected at study site using paper source casebooks which will then be data entered into the electronic CRF database unless transmitted to the Sponsor or designee electronically (e.g., laboratory data). The Investigator is responsible for verifying that data entries are accurate and correct by physically or electronically signing the CRF.

The Investigator must maintain accurate documentation (source data) that supports the information entered in the CRF. This can be paper source and/or eSource.

The Investigator must permit study-related monitoring, audits, REC review, and regulatory agency inspections and provide direct access to source data documents. Monitoring details describing strategy (e.g., risk-based initiatives in operations and quality such as Risk Management and Mitigation Strategies and Analytical Risk-Based Monitoring), methods, responsibilities, and requirements, including handling of noncompliance issues and monitoring techniques (remote or on-site monitoring) are provided in the Monitoring Plan.

Study monitors will perform ongoing source data verification to confirm that data entered into the CRF by authorized study site personnel are accurate, complete, and verifiable from source documents; that the safety and rights of participants are being protected; and that the study is being conducted in accordance with the currently approved protocol and any other study agreements, ICH GCP, and all applicable regulatory requirements.

Records and documents, including signed ICFs, pertaining to the conduct of this study must be retained by the Investigator during the retention period as agreed with the Sponsor and as required by local regulations or institutional policies.

#### **10.1.8.** Source Documents

Source documents provide evidence for the existence of the participant and substantiate the integrity of the data collected. Source documents are filed at the Investigator's site.

Data reported on the CRF or entered in the electronic CRF that are transcribed from source documents must be consistent with the source documents or the discrepancies must be explained. The Investigator

may need to request previous medical records or transfer records, depending on the study. Also, current medical records must be available.

Definition of what constitutes source data for the study can be found in the Source Data Agreement.

#### 10.1.9. Study Discontinuation

The Sponsor reserves the right to temporarily suspend or discontinue the study for any reason at any time. In addition, the study may be stopped at any time if, in the opinion of the PI, the safety data suggest that the medical safety of participants is being compromised.

If the study is suspended or terminated for safety reason(s), the Sponsor will promptly inform the PI, and will also inform the regulatory authorities of the suspension or termination of the study and the reason(s) for the action.

The Pl/Investigator is responsible for promptly informing the REC and providing the reason(s) for the suspension or termination of the study.

If the study is prematurely terminated, all study data must be returned to the **Sponsor**. In addition, the study site must conduct final disposition of all unused IMPs in accordance with **the Sponsor**'s procedures for the study.

Termination of the clinical trial may also be initiated by the MHRA or the REC.

#### **10.1.10.** Publication Policy

By signing the study protocol, the PI agrees that the results of this study may be used for the purposes of national and international registration, publication, and information for medical and pharmaceutical professionals by the Sponsor.

If necessary, the authorities will be notified of the PI's name, address, qualifications, and extent of involvement. In order to allow the use of the information derived from this clinical study, the PI understands that he has an obligation to provide complete test results and all data developed during this study to the Sponsor.

If the study is to be published, the Sponsor and hVIVO may jointly prepare and co-author manuscript(s) that could result from the clinical trial. In the case the Sponsor acts as fully responsible for the publication, the Sponsor agrees to allow the PI time to review all manuscripts and abstracts prior to submission for publication. The Sponsor reserves the right to include the report of this study in any regulatory documentation or submission or in any informational materials. The Sponsor also reserves the right to delete any confidential information from any proposed manuscripts prior to submission for publication. Confirmation of study specific arrangements can be found in the clinical study agreement.

Verbal or written discussion of results prior to study completion and full reporting should only be undertaken with written consent from the Sponsor.

# **10.2.** Appendix 2: Clinical Laboratory Tests

The tests detailed in Table 7 will be performed by the central laboratory.

Protocol-specific requirements for inclusion or exclusion of participants are detailed in Section 5 of the protocol.

Additional tests may be performed at any time during the study as determined necessary by the Investigator or required by local regulations.

Laboratory Assessments	Parameters	
Haematology	Platelet count. White blood cell (WBC) count (absolute) WBC differential: Neutrophils Lymphocyte Monocytes Eosinophils Basophils Red blood cell (RBC) count Reticulocyte count (% and absolute) Haemoglobin Haematocrit Mean corpuscular volume (MCV) Mean corpuscular haemoglobin (MCH) MCH concentration (MCHC)	
Coagulation	Prothrombin time (PT) Activated Partial Thromboplastin Time (APTT)	
Biochemistry	Sodium Potassium Glucose (random) Albumin Chloride Bicarbonate Calcium Uric acid Total protein Creatinine Total, direct, and indirect bilirubin Inorganic phosphate Blood urea nitrogen C-reactive protein (CRP) Gamma glutamyl transferase (GGT) Alkaline phosphatase (ALP) Alanine aminotransferase (ALT) Lactate dehydrogenase	

 Table 7: Protocol-Required Safety Laboratory Assessments

Laboratory Assessments	Parameters
	Aspartate aminotransferase (AST)
	Urea
	Thyroid Stimulating Hormone (TSH) at screening only
Thyroid function	Thyroxine at screening only
	Creatine Kinase (CK)
Cardiac enzymes	Troponin (T)
	Colour
	Specific gravity
	Appearance
	рН
Routine urinalysis	Presence of blood, glucose, leukocytes, ketones, nitrites, proteins,
	urobilinogen, bilirubin by dipstick
	Microscopy, culture, and sensitivity (MCS) examination (If the
	dipstick yields clinically significant abnormal results)
	Follicle stimulating hormone (FSH)*
	β-human chorionic gonadotrophin (β-hCG)
	Glycated haemoglobin A1c (HbA1c)**
	Total cholesterol
Other	TSH, free thyroxine (T4)
screening/eligibility	Antibodies against HIV-1 and HIV-2
tests	Hepatitis A immunoglobulin M (HepA)
	Hepatitis B surface antigen (HbsAg)
	Hepatitis C antibodies (HepC)
	Immunoglobulin A (IgA) antibodies**

\*Only for post-menopausal female participants \*\*Optional at PIs discretion

Investigators must document their review of each laboratory safety report.

Laboratory/analyte results that could unblind the study will not be reported to investigative sites or other blinded personnel until the study has been unblinded.

# 10.3. Appendix 3: Adverse Events: Definitions and Procedures for Recording, Evaluating, Follow-up, and Reporting

# 10.3.1. Adverse Event

#### **AE Definition**

An AE is defined as any untoward medical occurrence in participants. An AE can therefore be any unfavourable and unintended sign (including an abnormal laboratory finding), symptom, or disease temporally associated with the use of an IMP, whether or not considered related to the IMP, or for the purposes of HVC studies, the Challenge virus.

#### Events Meeting the AE Definition

- Exacerbation of a pre-existing illness.
- Increase in frequency or severity of a pre-existing episodic condition.
- A condition detected or diagnosed after IMP or inoculum administration even though it may have been present prior to the start of the study.
- A complication that occurs during a hospitalisation.
- A clinically significant change in laboratory parameter.

#### Events NOT Meeting the AE Definition

- Medical or surgical procedures (e.g., surgery, endoscopy, tooth extraction, transfusion); the condition that leads to the procedure is an AE.
- Pre-existing disease or conditions present or detected prior to start of IMP or Challenge virus inoculation administration that does not worsen (including screening findings such as abnormal laboratory results).
- Hospitalisation for elective surgery, social and/or convenience admissions provided they are arranged before the start of IMP administration.
- Over-administration of either the Challenge virus, IMP or concomitant medication without any signs or symptoms.
- An uncomplicated pregnancy or an induced elective abortion to terminate a pregnancy without medical reason.
- Typical/normal viral symptoms on symptom diary cards
- Procedural related events may be noted during the study whilst conducting nasal sampling (collection of nasal wash samples or nasopharyngeal swabs), specifically:
  - Nasal discomfort/irritation
  - Nasal abrasions
  - Nasal epistaxis

o Sneezing

• Watery eyes

When mild in nature and as expected in the opinion of the PI or Delegated Physician, these events will not be reported as AEs.

# 10.3.2. Adverse Drug Reaction

An adverse drug reaction is any untoward and unintended response in a participant to an IMP which is related to any dose administered to that participant.

'Response' in this context means that a causal relationship between a medicinal product and an AE is at least a reasonable possibility.

All AEs assessed by either the reporting Investigator or the Sponsor as having a reasonable causal relationship to a medicinal product qualify as adverse drug reactions. The expression 'reasonable causal relationship' means to convey in general that there is evidence or argument to suggest a causal relationship.

# 10.3.3. Unexpected Adverse (Drug) Reaction

An "Unexpected Adverse (Drug) Reaction" means an AR, the nature and severity of which is not consistent with the information about the medicinal product in question set out:

(a) In the case of a product with a marketing authorisation, in the Summary of Product Characteristics for that product,

(b) In the case of any other IMP, in the Investigator's Brochure relating to the trial in question'.

# 10.3.4. Serious Adverse Event

SA	SAE Definition			
AS	A SAE is defined as any untoward medical occurrence that, at any dose:			
a.	Results in death.			
b.	Is life-threatening.			
risk	The term 'life-threatening' in the definition of 'serious' refers to an event in which the participant was at risk of death at the time of the event. It does not refer to an event, which hypothetically might have caused death, if it were more severe.			
c.	Requires inpatient hospitalization or prolongation of existing hospitalization.			

• Hospitalisation for elective treatment of a pre-existing condition that did not worsen from baseline is not considered an AE.

#### d. Results in persistent disability/incapacity.

- The term disability means a substantial disruption of a person's ability to conduct normal life functions.
- This definition is not intended to include experiences of relatively minor medical significance such as uncomplicated headache, nausea, vomiting, diarrhoea, influenza, and accidental trauma (e.g., sprained ankle) which may interfere with or prevent everyday life functions but do not constitute a substantial disruption.

#### e. Is a congenital anomaly/birth defect.

f. Is an important medical event:

- Important medical events' some medical events may jeopardise the participant or may require an intervention to prevent one of the above characteristics/consequences. Such events should also be considered as 'serious' in accordance with the above definition.
- Medical judgement should be exercised in deciding whether an AE/AR is serious. Important AEs/ARs that are not immediately life threatening or do not result in death or hospitalisation but may jeopardise the participant or may require intervention to prevent one of the other outcomes listed in the definition above occurring, should also be considered serious. Details of the SAE must be provided.

# 10.3.5. Suspected Unexpected Serious Adverse Reaction

A SUSAR is 'a serious AR, the nature and severity\* of which is not consistent with the information about the medicinal product in question, as defined in the Investigator's Brochure relating to the trial in question.

Medical events will be assessed for expectedness against the Reference Safety Information section of the Investigator's Brochure or equivalent. Any changes to the Reference Safety Information will be deemed as a change to the risk/benefit profile and will require a substantial amendment to be submitted to the MHRA. This amendment must be approved before the changes are implemented in the study.

\*The term 'severity' is used here to describe the intensity of a specific event. This is not the same as 'serious' which is based on participant/event outcome or action criteria.

# 10.3.6. Recording, Assessment and Follow-up of AE and/or SAE

# 10.3.6.1. AE and SAE Recording

All AEs and SAEs will be collected from the time of written informed consent until study completion/final study contact or until the resolution of the AE. AEs will be fully recorded in the source documents as they are reported whether spontaneously volunteered by a participant or in response to questioning about wellbeing at each face-to-face study visit and during telephone calls. Enquiries about AEs should cover the period between the previous and current visit.

The following are examples of open ended, non-leading questions that may be used to obtain this information:

- How are you feeling?
- Have you had any medical problems since your last visit/assessment?
- Have you taken any new medicines, other than those given to you in this study, since your last visit/assessment?

Following the reporting of AEs and concomitant medication, the Investigator should assess the participant's eligibility to continue in the study.

The PI will record all relevant information regarding an AE/SAE in the source documents and evaluate AEs using the following guidelines:

- Description of events (if the event consists of a cluster of signs and symptoms, a diagnosis should be recorded)
- Seriousness
- Severity (or grade)
- Onset date and time
- Frequency
- Date and time of resolution (or 'continuing' if unresolved)
- Action taken
- Concomitant medication
- Clinical outcome
- Relationship or causality (IMP/Challenge virus/ study procedures/ concomitant medication/other).

Any clinically significant abnormal laboratory result, vital sign or other measure will be followed until it returns to normal or baseline values, stabilises, or is judged by the Investigator to be no longer clinically significant.

If an AE is not resolved at the end of the study, the AE should be followed until it has resolved or (in the case of pregnancy) the pregnancy has been terminated (including spontaneous abortion), resulted in a birth, or a decision has been made by the Sponsor that no further follow-up is required.

Even if the AE or SAE is assessed by the PI as not reasonably attributable to the Challenge virus, its occurrence must be fully documented in the source notes.

#### 10.3.6.2. Assessment

#### **Description**

If the event consists of a cluster of signs and symptoms, a diagnosis should be recorded (e.g., gastroenteritis) rather than each sign and symptom.

#### Onset and end

The dates and times of the onset and end of the event should be recorded.

#### Assessment

#### Challenge Virus Symptoms

The Investigator will assess, and review Challenge virus related symptoms recorded in participants' hVIVO symptom diary cards. Symptoms greater than Grade 0 will be expected and presumed to represent virus infection consequent to Viral Challenge and will not be additionally captured as AEs unless they meet the definition of an AE and are deemed to be clinically significant (in the opinion of the Investigator) to be classed as AEs.

Following Viral Challenge all unexpected (in the opinion of the Investigator) symptoms post inoculation will be captured as AEs, along with all other occurrences that meet the criteria for an AE.

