#### 2.3.1.1. Risks of SAB-176

SAB-176 is currently concluding a Phase 1 clinical trial (ClinicalTrials.gov identifier: NCT04471038). All participants have been infused with no serious adverse events (SAEs) reported through the highest dose cohort of 50 mg/kg and it appears to be safe and well tolerated. A previous Phase 1 study of SAB-301 (anti-Middle Eastern Respiratory Syndrome virus immunoglobulin) also derived from Tc bovines was shown to be safe and well tolerated at the highest dose of 50 mg/kg (ClinicalTrials.gov identifier: NCT02788188). It is anticipated that the risks for this Phase 2a study will be similar to the Phase 1 studies of SAB-176 and SAB-301 and the use of hIVIg with some unique considerations for proteins of animal origin as discussed below.

Based on hIVIg, common side effects may include:

- headache
- injection site reaction
- nausea
- urticaria
- fatigue
- arthralgia
- pyrexia.

Less common side effects may include:

- vomiting
- back pain
- rash.

Serious side effects seen with hIVIg that could be seen with SAB-176 include:

- Hyperproteinaemia, with resultant changes in serum viscosity and electrolyte imbalances may
  occur in patients receiving IVIg therapy (Steinberger et al. 2003). Humans routinely receive up to
  1 to 2 grams/kg of hIVIg to treat Guillain-Barre syndrome and other immune related neuropathies.
  Therefore, the addition of 50 mg/kg IgG as SAB-176 is a relatively small amount and is unlikely
  to cause AEs related to increased viscosity.
- Aseptic Meningitis Syndrome has been reported with IVIg treatments, especially with high doses or rapid infusion. This risk is anticipated to be minimized given the low amount of protein and relatively slow infusion.
- Haemolysis, either intravascular or due to enhanced red blood cell (RBC) sequestration, can be seen with human IVIg. This risk is anticipated to be low given the lack of exposure of the cows to human RBC antigens.
- Volume overload has been reported with human IVIg. This risk is anticipated to be minimized given the low amount of protein and small total volumes administered.

There may be additional risks of SAB-176 given its animal origin. SAB-176 is a fully human IgG so it is anticipated the risk would be less, though there may be residual animal proteins. The most similar product would be Horse Heptavalent Botulism Antitoxin which is an equine derived non-human polyclonal IgG polyclonal:

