To evaluate the safety of SAB-176, when compared to placebo.	
 
Clinical symptoms.
 
Occurrence of unsolicited AEs from IV infusion up to Day 28 follow-up.
 
Occurrence of SAEs from IV infusion up to Day 28 follow-up.
 
	
To evaluate the safety of the Influenza A/California/2009 H1N1 virus challenge model.	
 
Occurrence of unsolicited AEs related to the viral challenge from viral challenge (Day 0) up to Day 28 follow up.
 
Occurrence of SAEs related to the viral challenge from viral challenge (Day 0) up to Day 28 follow up.
 
Use of concomitant medications from viral challenge (Day 0) up to Day 28 follow up.
 
	
Tertiary/Exploratory*		
To further explore the effect of SAB-176, in reducing the incidence of influenza illness due to Influenza A/California/2009 H1N1 virus, compared to placebo.	
 
Upper Respiratory Tract illness,
 
Lower Respiratory Tract illness,
 
Systemic Illness,
 
Febrile Illness,
 
Mild to moderate symptoms.
 
	
• To explore the Minimal Clinically Important Difference (MCID) in instrument change (e.g., symptom diary cards).	
 
The average amount of instrument-assessed change for all participants who rate themselves as "a little better" or "somewhat better.
 
Additional endpoints may be considered for this objective and added at a later stage.
 
	

Objectives	Endpoints
• To explore the effect of SAB-176, in reducing the incidence of infection due to Influenza A/California/2009 H1N1, virus compared to placebo.	
 
Influenza viral infection rates in upper respiratory samples by qRT-PCR and cell culture.
 

• To further explore the safety of the Influenza A/California/2009 H1N1 virus challenge model.	
 
Occurrence of haematological and biochemical laboratory abnormalities during the quarantine period.
 

• To explore the utility of wearable continuous monitoring for assessing Influenza A/California/2009 H1N1 virus infection/disease.	
 
Measures captured by continuous monitoring may be explored in relation to Influenza challenge.
 

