#### Table 5: Study Stopping Rules

Status	Criterion	Procedure
1	A report has been received of one (or more) SUSAR(s) in any, one (or more) participant(s).	If such a status occurs at any point during the study, then further administration of SAB-176 will not take place. The PI and the SME will review the data and make decisions on whether it is appropriate to recommence dosing (approval of a substantial amendment from the competent authorities is required) or terminate the study.
2	No SUSAR have been reported but an overall pattern of clinical changes or symptoms exists, attributed to the IMP, which may appear minor or moderate in terms of individual AEs, but which collectively represent a concern for safety.	If such a status occurs at any point during the study, then further administration of IMP will not take place. The PI and the SME will review the data and decide on whether it is appropriate to recommence dosing (approval of a substantial amendment from the competent authorities is required) or terminate the study.
3	Unexpected virus-related SAE or unexpected virus-related AEs of clinical concern have been reported following HVC. *Expectedness will be assessed by referring to the Challenge virus dossier.	If such a status occurs at any point during the study, then the PI and the SME will review the data and decide based on expectedness* of the viral event. If the event is unexpected, further administration of the virus will not take place. The PI and the SME will review the data and decide on whether it is appropriate to recommence inoculation (approval of a substantial amendment from the competent authorities is required) or terminate the study.

In any event, participant follow-up should continue until resolution or stabilisation of AEs and final follow-up on Day 28 (±3 days).

Further enrolment into the study may be either temporarily or permanently discontinued if:

- An unacceptable number of severe or life-threatening exacerbations take place (as determined by the PI).
- If two or more (or a group of participants) experience clinically significant life-threatening AEs that are deemed to be significant by the PI.

Development of a group or cluster of clinically significant AEs that represent a safety risk to participants that are deemed to be significant by the PI.

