# 8.9. Tympanic Temperature

The study specific normal range for tympanic temperature is detailed in Appendix 4. The severity of out of normal range values will be assigned using the DMID toxicity scale as a guide.

Temperature may be more frequently monitored in quarantine if appropriate.

Following viral challenge, pyrexia will be expected and presumed to represent virus infection consequent to viral challenge and will not be additionally captured as an AE unless it meets the definition of an AE and is deemed to be clinically significant (in the opinion of the Investigator) to be classed as an AE.

Following viral challenge all unexpected (in the opinion of the Investigator) pyrexia will be captured as an AE, along with all other occurrences that meet the criteria for an AE.

Febrile illness is defined as any occurrence of temperature ≥37.9°C.

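### After the Day 1 infusion, headache, tiredness, joint ache and fever are presumed viral by default, so the SAB-176 v placebo AE comparison is likely to under-count mild reactions of these types

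*Combined protocol and SAP*

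**What the plan says.** Challenge is on Day 0 and the infusion on Day 1 (Section 6.1). Section 2.3.1.1 expects the risks of SAB-176 to resemble those of human IVIg, and under "Based on hIVIg, common side effects may include" it lists seven reactions.

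For the diary, Section 10.3.6.2 (Challenge Virus Symptoms) sets the default: "Symptoms greater than Grade 0 will be expected and presumed to represent virus infection consequent to Viral Challenge and will not be additionally captured". By default, then, no AE is recorded. The same sentence of the protocol gives an exception: "unless they meet the definition of an AE and are deemed to be clinically significant (in the opinion of the Investigator"). The next paragraph adds a second route. Symptoms that the Investigator regards as unexpected are covered, in that such "symptoms post inoculation will be captured as AEs, along with all other occurrences that meet the criteria for an AE".

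Fever follows the same pattern: "Following viral challenge, pyrexia will be expected and presumed to represent virus infection consequent to viral challenge" (Section 8.9, repeated under Temperature in 10.3.6.2), with the same two routes to capture. Section 10.3.1 also places "Typical/normal viral symptoms on symptom diary cards" among the events that are not AEs.

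The non-serious safety endpoint for SAB-176 is "Occurrence of unsolicited AEs from IV infusion up to Day 28 follow-up" (Section 3). Section 9.4.7 tabulates reported AEs by arm. Its list of other safety data does not include the diary.

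**The concern.** A reaction to the infusion would appear on Day 1 or soon after, inside the period when the protocol attributes such symptoms to the virus. If a mild headache or ache is presumed viral, it does not become an AE. It then never reaches the causality assessment that Section 10.3.6.5 requires for each AE. The presumption decides causality before anyone assesses it.

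The presumption also takes no account of infection status. Table 1 gives about a 65% chance of infection, so roughly 30 × 0.35 = 10.5 participants in an arm of 30 might be uninfected, and their symptoms are still presumed viral.

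At stake is the secondary objective of comparing the safety of SAB-176 with placebo. No solicited infusion-reaction endpoint stands in for the missing events. In the protocol the diary feeds symptom scores and illness definitions, where a product reaction would count as influenza symptom burden.

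**Working it through.** No stated figure in the plan tests this point, so the check sets the sections side by side and then shows how under-capture acts.

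**Step 1. Overlap.** Reactions from Section 2.3.1.1 against the 13 diary items in Section 8.11 and temperature in Section 8.9:

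| Common IVIg reaction | Matching viral item | Default |
|---|---|---|
| Headache | Headache | Presumed viral |
| Fatigue | Malaise/tiredness | Presumed viral |
| Arthralgia | Muscle and/or joint ache | Presumed viral |
| Pyrexia | Temperature; chilliness/feverishness | Presumed viral |
| Nausea | None | Normal AE capture |
| Urticaria | None | Normal AE capture |
| Injection site reaction | None | Normal AE capture |

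Four of seven fall under the presumption and three do not. The less common reactions (vomiting, back pain, rash) also have normal capture.

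**Step 2. What filters.** The AE definition in Section 10.3.1 covers any untoward symptom in temporal association with the IMP, whatever its cause. Most of these symptoms would therefore meet it, and the working filter is the Investigator's view of clinical significance, for which no criterion is given. The route for unexpected symptoms helps little, because these symptoms are declared expected after challenge. The closing clause, which captures all other occurrences meeting AE criteria, sits awkwardly with both the filter and the non-AE list.

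**Step 3. Effect on the arm difference.** Let r be the true excess of these reactions on SAB-176, p the placebo rate, and c the fraction of events that pass the filter, equal in both arms. Then observed difference = c(p + r) − cp = c × r.

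The values p = 5%, r and c below are assumptions, not document figures; 30 per arm is from Section 9.2. At r = 20%:

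| c | Expected AEs, SAB-176 v placebo | Difference | Fisher power |
|---|---|---|---|
| 1 | 30 × 0.25 = 7.5 v 30 × 0.05 = 1.5 | 20 points | 44% |
| 0.5 | 3.8 v 0.8 | 10 points | 9% |
| 0.25 | 1.9 v 0.4 | 5 points | 1% |

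Across the range of r: at 9%, power is 7% with full capture and under 1% at c = 0.5; at 40%, it is 95%, 49% and 8% for c = 1, 0.5 and 0.25. The plan has no formal AE test, so power is only a gauge of visibility.

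**Step 4. Would recording every diary symptom solve it?** With a viral background v in both arms, the SAB-176 rate is 1 − (1 − v)(1 − r) and the difference is r(1 − v). Taking v = 65% (the infection chance, assuming that every infection is symptomatic) and r = 20%: 1 − 0.35 × 0.80 = 0.72, a 7-point difference (power 5%). At v = 30% it is 14 points. If SAB-176 also cut viral symptoms by 40%, its background is 0.65 × 0.6 = 0.39. The rate is then 1 − 0.61 × 0.80 = 0.512, a net difference of about −14 points. Whole-quarantine diary totals can therefore hide reactions. A short window measured from a pre-infusion reference should do better if the viral background in it is lower, which the documents do not quantify.

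**The case against.** The strongest reply is that the exclusion is not absolute, applies equally to both arms under blinding, and belongs to an exploratory Phase 2a. Day 1 vital signs are taken before the infusion and at seven times up to 8 hours after its start (SoA note e), and Section 9.4.7 summarises vital signs by time and arm. Appendix 4 lists tympanic temperature with the vital signs, so fever may already be tabulated. Statistical detail is deferred to the SAP (Section 9.4.1).

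Much of this stands. But equal treatment does not cancel the problem, because Step 3 shows that c multiplies the difference. The SoA lists temperature apart from vital signs and schedules it only three times daily. Nothing in Section 9.4.7 covers headache, tiredness or joint ache outside reported AEs.

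A reader might also infer more than the documents support:

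- *That these symptoms are never recorded as AEs.* The exception and the route for unexpected symptoms both allow it.
- *That SAB-176 could look safer than placebo through its antiviral effect.* Viral-type symptoms are largely kept out of the AE table, so a later reduction in them can do little to lower the SAB-176 AE count.
- *That the Status 2 stopping criterion in Table 5 is disabled.* It speaks of events "which may appear minor or moderate in terms of individual AEs, but which collectively represent a concern for safety", but what it looks for is a pattern of clinical changes or symptoms attributed to the IMP. Section 7.5 has available clinical data reviewed, and the Investigator sees the diary cards.
- *That the 9% headache rate sizes the loss.* It gives 30 × 0.09 = 2.7 headaches and a 1 − 0.91^30 = 94% chance of at least one. But it belongs to an equine antitoxin, and Section 2.3.1.1 anticipates lower risk with a fully human IgG. It is not net of placebo and says nothing about the share captured.

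**Conclusion.** The point holds in a limited form. For four of the seven listed common reactions, non-serious events after the infusion reach the AE tables only if the Investigator judges them clinically significant or unexpected. The unsolicited-AE comparison is therefore likely to under-count mild reactions of these types and to shrink any true arm difference by the fraction captured.

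The size cannot be derived. The documents give neither a SAB-176 reaction rate nor a criterion for clinical significance, and the figures in Steps 3 and 4 rest on assumed values. The conclusion also assumes that the SAP, which is not in the text reviewed, adds no safety table from the diary. This is a cheap improvement to a secondary objective and does not affect the primary analysis.

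**What to change.** 1. **Add one descriptive table to the SAP, on the Safety Analysis Set, by arm.** Count participants with a new or worsened score for headache, malaise/tiredness, muscle/joint ache and chilliness/feverishness, and with tympanic temperature ≥37.9°C, relative to the pre-infusion Day 1 assessment. Pre-specify an early post-infusion window, for example the remaining Day 1 and the Day 2 assessments. With three assessments daily and the first on Day 1 taken before the infusion, that gives 2 + 3 = 5 scheduled assessments already collected. State whether a temperature needs a confirmatory repeat, since Appendix 6 requires one and Section 8.9 does not.
2. **Reconcile the AE definition and the non-AE list (Section 10.3.1) with the viral presumption (Sections 8.9 and 10.3.6.2)** for symptoms that start after the infusion.

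The cost is one table and some wording. The end of Day 2 is only an example and has no basis in the documents. Assessments after the infusion are not at fixed intervals from it. Viral symptoms in both arms will dilute an excess, and an antiviral effect could partly offset it, so the table should be read descriptively and without a test.
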